9.2. Discussion of Study Design

The primary endpoint is evaluating the long-term safety and tolerability of ACE-536 administration in patients with β -thalassemia who completed participation in A536-04. To support this endpoint, this study includes safety measurements that are considered standard for studies with investigational medications.

An open-label study, conducted in a limited number of patients, with protocol-specified procedures for dose reduction is considered appropriate for a long-term safety study in this target patient population. Individualization of dose level, using dose titration rules based on hemoglobin response and dose reduction rules based on safety information will maximize the proportion of patients having an erythroid response while maintaining safety.

Secondary endpoints were selected to evaluate the impact of ACE-536 on efficacy and PD parameters, including effects on hematologic parameters and on complications of thalassemia.

The initial dose level of 0.8 mg/kg has been selected for patients with treatment interruption based upon data from the ongoing A536-04 study. Dose levels utilized in this study will not exceed maximum dose levels tested in study A536-04.

9.3. Selection of Study Population

9.3.1. Transfusion Status

- For patients without treatment interruption patient transfusion status (NTD or TD) will carry-over from the base study A536-04.
- For NTD patients with treatment interruption, patient transfusion status will be reassessed prior to C1D1 of study A536-06.
 - NTD patients with treatment interruption are defined as patients who require transfusion of < 4 units of RBCs over the 8 weeks prior to Cycle 1 Day 1 of study A536-06.
- For TD patients with treatment interruption, patient transfusion status will carry-over from the base study A536-04.

9.3.2. Inclusion Criteria

All patients must meet the following criteria:

1. Completion of the treatment period in the base study A536-04.
2. Females of child bearing potential (defined as sexually mature women who have not undergone hysterectomy or bilateral oophorectomy, or are not naturally postmenopausal ≥ 24 consecutive months) must have negative urine or blood pregnancy test prior to enrollment and use adequate birth control methods (abstinence, oral contraceptives, barrier method with spermicide, or surgical sterilization) during study participation and for 12 weeks following the last dose of ACE-536. Males must agree to use a latex condom during any sexual contact with females of child-bearing potential during study participation and for 12 weeks following the last dose of ACE-536, even if he has undergone a successful vasectomy. Patients must be counseled concerning measures to be used to prevent pregnancy and potential toxicities prior to the first dose of ACE-536.
3. Patient is able to adhere to the study visit schedule, understand and comply with all protocol requirements.
4. Patient understands and is able to provide written informed consent.

All patients with treatment interruption must also meet the following criteria:

Patients with treatment interruption (defined as patients who complete the EOS visit for study A536-04 and are ≥ 28 days post EOS visit) must also meet the following criteria:

5. Mean hemoglobin concentration < 10.0 g/dL of 2 measurements (not influenced by RBC transfusion) (one performed within one day prior to Cycle 1 Day 1 and the other performed during the screening period [Day -28 to Day -1]) in NTD patients.
6. Adequate folate levels or on folate therapy.
7. Platelet count $\geq 100 \times 10^9/L$ and $\leq 1,000 \times 10^9/L$.
8. Aspartate aminotransferase (AST) or alanine aminotransferase (ALT) $< 3 \times$ upper limit of normal (ULN).
9. Serum creatinine $\leq 1.5 \times$ ULN.
10. Ejection fraction $\geq 50\%$ by Echocardiogram (ECHO) or Multi gated acquisition scan (MUGA).

9.3.3. Exclusion Criteria

All patients must not meet any of the following criteria:

1. Discontinuation/withdrawal from study A536-04 due to patient request, patient unwillingness or inability to comply with the protocol, pregnancy, use of prohibited medication (e.g., hydroxyurea), medical reason or AE, hypersensitivity reaction to the study drug, at the discretion of the sponsor, or loss to follow-up prior to completion of the treatment period.
2. Any clinically significant pulmonary (including pulmonary hypertension), cardiovascular, endocrine, neurologic, hepatic, gastrointestinal, infectious, immunological (including clinically significant allo- or auto-immunization) or

genitourinary disease considered by the investigator as not adequately controlled prior to Cycle 1 Day 1.

3. Symptomatic splenomegaly.
4. Splenectomy within 56 days prior to Cycle 1 Day 1.
5. Major surgery (except splenectomy) within 28 days prior to Cycle 1 Day 1. Patients must have completely recovered from any previous surgery prior to Cycle 1 Day 1.
6. Patients receiving or planning to receive hydroxyurea treatment. Patients must not have had hydroxyurea within 90 days of Cycle 1 Day 1.
7. For patients with treatment interruption: Iron chelation therapy if initiated within 56 days prior to Cycle 1 Day 1.
8. Cytotoxic agents, systemic corticosteroids, immunosuppressants, or anticoagulant therapy such as warfarin or heparin within 28 days prior to Cycle 1 Day 1 (prophylactic aspirin up to 100 mg/day and low molecular weight (LMW) heparin for superficial venous thrombosis (SVT) is permitted).
9. Treatment with another investigational drug (including sotatercept [ACE-011]) or device, or approved therapy for investigational use \leq 28 days prior to Cycle 1 Day 1, or if the half-life of the previous investigational product is known, within 5 times the half-life prior to Cycle 1 Day 1, whichever is longer at any time between the end of treatment of the base study A536-04 and Cycle 1 Day 1.
10. Known positive for human immunodeficiency virus (HIV), active infectious hepatitis B (HBV) or active infectious hepatitis C (HCV).
11. Uncontrolled hypertension defined as systolic blood pressure (SBP) \geq 150 mm Hg or diastolic blood pressure (DBP) \geq 100 mm Hg.
12. Known history of thromboembolic events \geq grade 3 according to the National Cancer Institute-Common Terminology Criteria for Adverse Events (NCI-CTCAE) v.4.0 (current active minor version).
13. Pregnant or lactating females.
14. History of severe allergic or anaphylactic reactions or hypersensitivity to recombinant proteins or excipients in the investigational drug.
15. Any other condition not specifically noted above which, in the judgment of the investigator, would preclude the patient from participating in the study.

9.4. Patient Treatment Discontinuation and Withdrawal Criteria

Patients will be informed that they have the right to withdraw from the study at any time for any reason without prejudice to their medical care.

A patient may be discontinued from treatment for any of the following reasons:

- Patient's request
- Patient's unwillingness or inability to comply with the protocol

- Pregnancy
- Use of prohibited medication (e.g. hydroxyurea)
- Medical reason or AE, at the discretion of the investigator and/or the medical monitor
- Hypersensitivity reaction to study drug
- At the discretion of the sponsor (e.g. termination of the study or a dose level)

A patient may be withdrawn from the study for any of the following reasons:

- Patient's request
- Patient's unwillingness or inability to comply with the protocol
- Death
- Loss to follow-up
- At the discretion of the sponsor (e.g., termination of the study).

The reasons for study withdrawal and treatment discontinuation must be recorded in the patient's CRF. The investigator must notify the sponsor, the medical monitor and the contract research organization (CRO) immediately when a patient has been discontinued/withdrawn due to an AE. Patients who discontinue treatment early should complete the end of treatment (EOT) follow-up visit at the time of discontinuation and then complete the EOS follow-up visit approximately 28 days later.

The investigator must notify the sponsor and the CRO when a patient has been discontinued/withdrawn for reasons unrelated to the study or study drug (e.g., withdrawn consent, lost to follow up).

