23 **Transfusion frequency/volume:** Transfusion history will be collected from the EOS visit in study A536-04 through the C1D1 visit of A536-06 as available; TD patients will have a “pre-transfusion hemoglobin threshold” for requiring transfusion during the study which will be determined based on transfusion history. For TD patients without treatment interruption, baseline pre-transfusion hemoglobin threshold will be the mean of all documented pre-transfusion hemoglobin values during the 12 weeks prior to C1D1 of base study A536-04 or study A536-06 (for TD patients with treatment interruption). During treatment, if the pre-transfusion hemoglobin level is increased by ≥ 1 g/dL compared to the baseline pre-transfusion hemoglobin threshold for that patient, transfusion should be delayed by a minimum of 7 days and/or the number of units transfused should be reduced by 1 or more RBC units. Patients may be transfused at the investigator’s discretion for symptoms related to anemia or other requirements (e.g., infection).

24 **Adverse events:** Patients should be monitored for AEs throughout the study. All AEs and abnormal findings that might require modification of dosing (see [Section 10.8](#)) should be reviewed prior to dosing to ensure that the patient is still eligible to receive additional doses of ACE-536.

25 **End of Treatment (EOT):** Should be performed 28 days (± 7 days) after the last dose of ACE-536. Patients who discontinue treatment early should complete the EOT visit at the time of discontinuation.

26 **Post-Treatment Follow-Up (PTFU):** Should be performed 2 months (± 7 days) after the last dose of ACE-536.

27 **Long-Term Follow-Up (LTFU):** Should be performed every 6 months (± 14 days) after the last dose of ACE-536 for 3 years after the last dose of ACE-536 to monitor for presence of malignancy and pre-malignancy, as per standard of care.

28 **End of Study (EOS):** Should be performed 3 years after the last dose of ACE-536.

29 **Cycles 6 through 17:** Procedures and visits for Cycles 6 through 9, 10 through 13, and 14 through 17 follow the same procedures and visits as scheduled for Cycles 2 through 5, with some exceptions as noted above.

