12.5. Long-Term Follow-Up Visits

- LTFU visits should occur beginning every 6 months (\pm 14 days) after the last dose of ACE-536 for 3 years after the last dose of ACE-536.

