12.6. End of Study Visit

- The EOS visit should occur approximately 3 years after the last dose of ACE-536.
- Physical exam should include an optional evaluation of gonadal size of male patients.

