3.2. Treatment Discontinuation

Patients were informed that they have the right to withdraw from the study at any time for any reason without prejudice to their medical care.

A patient may be discontinued from treatment for any of the following reasons:

- Patient's request
- Patient's unwillingness or inability to comply with the protocol
- Pregnancy
- Use of prohibited medication (e.g., hydroxyurea)
- Medical reason or adverse event, at the discretion of the investigator and/or the medical monitor
- Hypersensitivity reaction to study drug
- At the discretion of the sponsor (e.g., termination of the study or a dose level)

A patient may be withdrawn from the study for any of the following reasons:

- Patient's request
- Patient's unwillingness or inability to comply with the protocol
- Death
- Loss to follow-up
- At the discretion of the sponsor (e.g., termination of the study)

Patients who discontinue treatment early should complete the end of treatment (EOT) follow-up visit at the time of discontinuation and then complete the end of study (EOS) follow-up visit approximately 28 days later.

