A transfusion amount reported in “mL” will be converted to “units” according to medical review.

End of Treatment (EOT)

Procedures and evaluations for the end of treatment visit should be performed 28 days (± 7 days) after the last dose of ACE-536.

Post-Treatment Follow-Up (PTFU)

The PTFU visit should occur 2 months (± 7 days) after the last dose of ACE-536. If a patient has a positive ADA result at the last visit, the patient may be asked to return for additional ADA testing every three months, until a negative result is obtained or the result is considered to be stabilized.

Long-Term Follow-Up (LTFU)

LTFU visits should occur beginning every 6 months (± 14 days) after the last dose of ACE-536 for 3 years after the last dose of ACE-536.

End of Study (EOS)

Procedures and evaluations for the end of study visit should be performed approximately 3 years after the last dose of ACE-536.

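### Protocol 9.4 and SAP 3.2 close early stoppers about 28 days after end of treatment, contradicting the 3-year malignancy follow-up set everywhere else

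*Protocol*

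**What the plan says.** Two sets of current text give different EOS dates for a patient who stops treatment early.

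**Short path.** Protocol 9.4 puts EOT "at the time of discontinuation and then complete the EOS follow-up visit approximately 28 days later". SAP 3.2 gives the same order: EOT at discontinuation, "then complete the end of study (EOS) follow-up visit approximately 28 days later".

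**Three-year path.**
- Protocol Section 2, footnote 27, schedules LTFU six-monthly "for 3 years after the last dose of ACE-536 to monitor for presence of malignancy and pre-malignancy, as per standard of care". Footnote 28 says of EOS: "Should be performed 3 years after the last dose of ACE-536".
- Protocol 12.5: "LTFU visits should occur beginning every 6 months", running for 3 years from the last dose. Protocol 12.6: "The EOS visit should occur approximately 3 years after the last dose of ACE-536".
- SAP 5.1: "Procedures and evaluations for the end of study visit should be performed approximately 3 years after the last dose of ACE-536".
- Protocol 9.1 plans a 36-month follow-up period, and 11.3 requires new malignancies and premalignant lesions to be reported through 3 years of follow-up.

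None of the 3-year rules excepts early stoppers. Footnote 25 and Protocol 12.3 do address them, but change only the EOT date: "Patients who discontinue treatment early should complete the EOT visit at the time of discontinuation".

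**Related text.** Protocol 14.5 and 14.5.1 end AE and SAE recording 56 days after the last dose and call that point the EOS visit. Protocol 14.6 describes AE recording as running to the end of the treatment period.

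**The concern.** Section 9.4 is the protocol's section on discontinuation, and the only protocol text giving an EOS date specifically for early stoppers. A coordinator handling a discontinuation could reasonably follow it and close the patient about four weeks after EOT.

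The primary objective is long-term safety, and new malignancy or pre-malignancy is the AE of special interest (Protocol 14.1). In the Schedule, malignancy monitoring is marked at LTFU and EOS. A patient closed under 9.4 would have one early check, at that EOS, and none at the six-monthly points. The missing follow-up would be concentrated in patients who stopped, including some who stopped for adverse events, so it would not be missing at random with respect to safety. The follow-up listing in SAP 5.8.6 would be short for the same patients. Some would also be closed before the 56-day AE window in 14.5 had run out.

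**Working it through.** **The plan's own figure.** Protocol 9.1 gives up to 97 months: 1 (screening) + 60 (treatment) + 36 (follow-up) = 97. It reproduces, and it includes the full 3 years of follow-up.

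**Inputs**
- EOS under 9.4 and SAP 3.2: EOT day + 28.
- EOS under footnote 28, 12.6 and SAP 5.1: 3 years = 3 × 365.25 = 1,095.75 days after the last dose.
- LTFU: every 6 months ± 14 days (footnote 27, 12.5), so 36/6 = 6 time points, the last coinciding with EOS.
- PTFU: 2 months ± 7 days (footnote 26).
- AE window: 56 days after the last dose (14.5).
- Assumption: EOT falls 0 to 35 days after the last dose. Zero is a stop on the dosing day; 35 is the routine 28 days plus the 7-day window. The documents set no upper limit for early stoppers.

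**EOS date under 9.4.** 0 + 28 = day 28; 35 + 28 = day 63.

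**Post-treatment follow-up lost**
- EOS at day 28: 1 − 28/1,095.75 = 97.4%, or (1,095.75 − 28)/365.25 = 2.92 years.
- EOS at day 63: 1 − 63/1,095.75 = 94.3%, or (1,095.75 − 63)/365.25 = 2.83 years.

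**Loss counting time on treatment as observed.** For a stop at month m, the share lost is (1,095.75 − EOS day)/(30.4375m + 1,095.75). The denominator is that patient's time to stopping plus 3 years. Stop times are illustrative.

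| Stop at month | Share lost |
|---|---|
| 6 | 80.8% to 83.5% |
| 12 | 70.7% to 73.1% |
| 36 | 47.1% to 48.7% |
| 59 | 35.7% to 36.9% |

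**Six-monthly checks.** The first LTFU is nominally day 182.6 and at the earliest 182.6 − 14 = day 168.6. That is 168.6 − 63 = 106 to 168.6 − 28 = 141 days after the 9.4 EOS. Time points reached: 0 of 6.

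**Break-even.** For the 9.4 EOS to reach the first LTFU window, EOT would have to fall at 168.6 − 28 = about day 141 after the last dose.

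**PTFU.** The window is 60.9 ± 7, about day 54 to 68. If EOT is before about day 26 (53.9 − 28), the 9.4 EOS precedes even PTFU.

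**AE window.** Shortfall = max(0, 56 − EOS day). EOT on day 0: 28 days short. EOT on day 21, the next dosing day: EOS on day 49, 7 days short. EOT on day 28 or later: none.

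**Likely origin.** SAP Appendix 3 (base study A536-04), footnotes 12 and 13, places EOT at discontinuation and that study's final visit 28 days later; its EOS is 56 days after the last dose. The wording of 9.4 and the day-56 EOS labels in 14.5 and 14.5.1 fit that schedule, so carry-over is a reasonable inference.

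**The case against.** The strongest reply is that the rest of the protocol already protects follow-up, and 9.4 is a stale sentence.

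- Footnote a in 10.8 sends patients discontinued after more than two AE-related dose reductions through EOT, PTFU, LTFU and EOS.
- Sections 10.2 and 10.2.2 send patients who need an excluded medication or hydroxyurea into the follow-up period.
- The Schedule's EOT column covers discontinuation and is followed by PTFU, LTFU and a 3-year EOS. Sections 11 and 12 refer sites to that Schedule.
- The visit in 9.4 falls roughly where PTFU now sits, so it may simply never have been renamed.
- The malignancy reporting duty in 11.3 does not depend on visits.
- LTFU data are only listed and no hypothesis is tested, so no planned estimate changes.

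Much of this stands. It shows that 9.4 is an error rather than an intended shorter path, and that some stopping routes have explicit protection. It does not remove the conflict. The 10.8 route covers one reason for stopping, and the matching bullet in 10.7 lists only EOT and EOS. Other adverse-event stops have no LTFU-specific text, and no clause gives the Schedule precedence over 9.4. A reporting duty without visits is weak once a patient has been closed. On 14.6, its opening cross-reference to 14.5 softens the discrepancy, but its stated end point still differs.

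**Conclusion.** The concern holds. Each document contradicts itself on when an early stopper's EOS takes place. For a patient handled under 9.4, with EOT 0 to 35 days after the last dose, 2.83 to 2.92 years of the 3-year follow-up are lost, together with all six half-yearly malignancy time points. The loss of every six-monthly point would be avoided only if EOT came about 141 days or more after the last dose, as after a very long dose hold. For a patient handled under the Schedule the loss is zero.

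No study-level figure is possible: the documents give neither the number of early stoppers nor any sign of which text sites follow. The case for correction rests on the selective nature of the potential loss in a study whose primary purpose is long-term safety. It should be fixed.

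**What to change.** - In Protocol 9.4 and SAP 3.2, replace the clause placing EOS 28 days after EOT with: *then complete PTFU, LTFU and EOS as scheduled from the last dose*.
- In Protocol 14.5 and 14.5.1, delete the parenthetical naming day 56 as the EOS visit.
- In Protocol 14.6, state the 56-day AE window plus malignancy reporting through 3 years.
- Optional: add PTFU and LTFU to the synopsis dose bullets, Protocol 10.1 and 10.7, and the SAP 3.1 bullets. These are incomplete rather than contradictory.

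With the change, EOS for early stoppers returns to about day 1,096 and all six time points are kept. The cost is wording only, because every visit is already in the Schedule. Since the text affects safety follow-up, it needs a protocol amendment with ethics committee approval and regulatory submission under Protocol Section 19, and a matching revision of SAP 3.2.

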10. TREATMENT OF PATIENTS

10.1. Selection and Timing of Dose for Each Patient

Once a patient is enrolled, the appropriate dose of ACE-536 will be administered as an SC injection on Cycle 1 Day 1. Subsequent doses will be administered every 3 weeks on Day 1 of the cycle for up to 87 cycles. Patients may not exceed 87 cycles or 1825 days after first dose, whichever occurs first. The last dose of ACE-536 may not be administered after Day 1825, regardless of the number of cycles completed. Dose reductions may be required for individual patients as outlined in the Patient Dose Modifications Rules ([Section 10.8](#)). If a dose delay is required, the patient will return weekly for assessment of hematology results and AEs until the patient is eligible to receive the next dose of ACE-536. Patients will be asked to return to the clinic for two follow-up visits, occurring approximately 28 days and 56 days after their last dose of ACE-536. Dose level titration increases may also occur for individual patients as outlined in the Individual Dose Titration rules ([Section 10.9](#)). If a patient has a positive ADA result at the last visit, the patient may be asked to return for additional ADA testing every three months, until a negative result is obtained or the result is considered to be stabilized.

10.2. Concomitant Medications

During screening and throughout the study patients may take stable doses of medications for chronic conditions that are not specifically excluded by the protocol (see [Section 9.3](#)). If a patient requires treatment with any new medications that are specifically excluded by the eligibility criteria, the patient will be discontinued from the study and should complete the end of treatment visit and enter the follow-up period of the study. The investigator should consult the medical monitor regarding any questions about whether a new medication or dosage of existing medication would require the patient to discontinue from the study. For patients without treatment interruption, any concomitant medication ongoing at the time of EOT in A536-04 needs to be re-entered as a concomitant medication in A536-06. For patients with treatment interruption, concomitant medications will be collected beginning at study screening and will include all medications taken within 28 days prior to Cycle 1 Day 1.

10.2.1. Prohibited Concomitant Medications and Procedures

No concurrent treatments with any other investigational agent are allowed.

The following are not allowed during the treatment period: hematopoietic growth factors, anticoagulant therapies for deep vein thrombosis (DVT), and platelet aggregation inhibitors (with the exception of aspirin and LMW heparin). If a patient requires use of these therapies, the patient should be discontinued from the study treatment.

10.2.2. Other Treatments for β -Thalassemia

If treatment with hydroxyurea is required during the ACE-536 treatment period, the patient should be discontinued from treatment with study drug and complete the EOT visit and enter the follow-up period. Iron chelation therapy is allowed if initiated at least 56 days prior to C1D1. If iron chelation therapy is required during study treatment, patient should follow standard of care for management of iron chelation therapy.

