5.7. Efficacy Analyses

No formal hypothesis testing is planned. All efficacy endpoint will be performed using the ITT population.

In general, the below rules apply to the derivations of efficacy endpoints which utilize hemoglobin and RBC transfusion data unless specified otherwise:

- Hemoglobin measurements within 14 days following RBC transfusion will be excluded from the efficacy analysis.
- For each patient, all efficacy endpoints will be derived based on an analysis cutoff day, defined as the last dose + 56 days or the last date from transfusion record data, whichever is earlier.

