5.7.2. Secondary Efficacy Endpoints

5.7.2.1. Erythroid Response

Erythroid response rates will be defined as below for NTD and TD patients.

For NTD patients:

- The proportion of patients with a mean increase of ≥ 1.0 g/dL from pretreatment hemoglobin during any rolling 8 weeks
- The proportion of patients with a mean increase of ≥ 1.5 g/dL from pretreatment hemoglobin during any rolling 8 weeks
- The proportion of patients with a mean increase of ≥ 1.0 g/dL from pretreatment hemoglobin during any rolling 12 weeks
- The proportion of patients with a mean increase of ≥ 1.5 g/dL from pretreatment hemoglobin during any rolling 12 weeks
- The proportion of patients with a mean increase of ≥ 1.0 g/dL from pretreatment hemoglobin during any rolling 24 weeks
- The proportion of patients with a mean increase of ≥ 1.5 g/dL from pretreatment hemoglobin during any rolling 24 weeks
- The proportion of patients with a mean increase of ≥ 1.0 g/dL from pretreatment hemoglobin during weeks 13-24
- The proportion of patients with a mean increase of ≥ 1.5 g/dL from pretreatment hemoglobin during weeks 13-24
- The proportion of patients with a mean increase of ≥ 1.0 g/dL from pretreatment hemoglobin during weeks 37-48

- The proportion of patients with a mean increase of ≥ 1.5 g/dL from pretreatment hemoglobin during weeks 37-48

For TD patients:

- The proportion of patients who have $\geq 20\%$ reduction in RBC transfusion burden compared to pretreatment using rolling 8-week intervals
- The proportion of patients who have $\geq 33\%$ reduction in RBC transfusion burden compared to pretreatment using rolling 8-week intervals
- The proportion of patients who have $\geq 50\%$ reduction in RBC transfusion burden compared to pretreatment using rolling 8-week intervals
- The proportion of patients who have $\geq 20\%$ reduction in RBC transfusion burden compared to pretreatment using rolling 12-week intervals
- The proportion of patients who have $\geq 33\%$ reduction in RBC transfusion burden compared to pretreatment using rolling 12-week intervals
- The proportion of patients who have $\geq 50\%$ reduction in RBC transfusion burden compared to pretreatment using rolling 12-week intervals
- The proportion of patients who have $\geq 33\%$ reduction in RBC transfusion burden compared to pretreatment during weeks 13-24
- The proportion of patients who have $\geq 50\%$ reduction in RBC transfusion burden compared to pretreatment during weeks 13-24

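### The efficacy cutoff in SAP 5.7 ignores on-study splenectomy and, to a lesser extent, a switch to hydroxyurea or a growth factor, so later windows can be credited to ACE-536

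*Protocol*

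**What the plan says.** **Cutoff and exclusions.** SAP 5.7 sets one cutoff per patient for all efficacy endpoints, "defined as the last dose + 56 days or the last date from transfusion record data, whichever is earlier". The only data it removes are these: "Hemoglobin measurements within 14 days following RBC transfusion will be excluded from the efficacy analysis".

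**Response and duration.** SAP 5.7.2.1 scores NTD patients on the mean rise "from pretreatment hemoglobin during any rolling 8 weeks" and TD patients on the "reduction in RBC transfusion burden compared to pretreatment using rolling 8-week intervals". It adds rolling 12- and 24-week versions and fixed windows at weeks 13-24 and 37-48. Where a patient has several separate response periods, SAP 5.7.2.2 takes the longest.

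**Splenectomy.** Protocol 9.3.3 excludes "Splenectomy within 56 days prior to Cycle 1 Day 1". Protocol 10.2.1, which lists what is not allowed on treatment, does not name it. The SAP uses splenectomy as a baseline characteristic (5.4) and a subgroup factor (5.7.4). Non-medication procedures are coded and listed (5.6.3), with no effect on any derivation.

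**Hydroxyurea and growth factors.** Protocol 9.3.3 bars hydroxyurea within 90 days of entry. Protocol 10.2.2 says what happens "If treatment with hydroxyurea is required during the ACE-536 treatment period": study drug stops, the EOT visit is done, and the patient enters follow-up. Protocol 10.2.1 likewise ends study treatment if a hematopoietic growth factor is needed. Neither section says what happens to efficacy data collected afterwards. SAP 5.11 only lists prohibited medication as a deviation.

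**The concern.** The protocol treats recent splenectomy, hydroxyurea and growth factors as incompatible with a clean reading of ACE-536, at entry or by ending study treatment. The efficacy derivation does not carry that through. The study has no control group, so nothing in the data can separate the effect of the drug from that of a splenectomy in a window that follows one.

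The scoring rule makes this matter more. One qualifying window anywhere in follow-up is enough to make a responder, and the longest run sets the duration. A single period of transfusion relief after surgery, or on a replacement drug, is therefore enough. TD responder status also feeds the exploratory LIC comparison in SAP 5.7.2.7, so a misclassified patient is carried into a second analysis.

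**Working it through.** The plan is descriptive and has no sample size or power figure to reproduce. The check is window arithmetic plus one illustrative interval.

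**Inputs from the documents.** Cutoff and 14-day exclusion (SAP 5.7); windows of 56, 84 and 168 days (SAP 5.7.2.1); dosing every 21 days and no dose after Day 1825 (Protocol 10.1); EOT 28 ± 7 days after the last dose, or at the time of early discontinuation (Protocol 12.3).

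**1. Splenectomy while dosing continues.**
- Latest possible cutoff = 1825 + 56 = Day 1881, if transfusion records run that far.
- Window positions of w days wholly after a splenectomy on day s = 1881 − (s + w) + 1.
- For s = 365: 1,461 positions at 8 weeks, 1,433 at 12 weeks and 1,349 at 24 weeks.
- These are ceilings for a patient dosed to the end. Every such window is 100% post-splenectomy, and none is removed.

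**2. Tail after a switch of drug.** Days of the other drug inside a window = min(w, c − s), with data end c and start s counted from the last ACE-536 dose.

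| Data end c | Start s | Days | Share of 8 wk | Share of 12 wk | Share of 24 wk |
|---|---|---|---|---|---|
| 56 | 0 | 56 | 100% | 66.7% | 33.3% |
| 56 | 21 (next dose due) | 35 | 62.5% | 41.7% | 20.8% |
| 35 (latest scheduled EOT) | 0 | 35 | 62.5% | 41.7% | 20.8% |
| 35 | 21 | 14 | 25.0% | 16.7% | 8.3% |

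Examples for the first row, with evenly spread measurements assumed:
- An NTD patient with a mean rise of 0.5 g/dL over the last 28 on-drug days and 2.0 g/dL over the tail has (28 × 0.5 + 56 × 2.0)/84 = 1.5 g/dL, which meets the 12-week criterion.
- A TD patient with 12 units per 12 weeks at baseline may have 6 units at a 50% reduction. An unchanged 4 units in 28 days leaves 6 − 4 = 2 for the tail.

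**3. Direction.** The windows allowed now include every window that an earlier cut would allow. A rolling-window response requires at least one window to qualify, so the extra windows can add responders but never remove one. The longest observed response likewise cannot become shorter. This argument does not extend to fixed-week rates, mean changes or the Kaplan-Meier duration curve. Fixed-week rates are touched only if the event falls before or within those weeks.

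**4. Size per patient.** The TD/NTD split, the number of responders and the number of affected patients are not given. Assume 30 TD patients with 15 responders. One extra responder shifts the rate by 1/30 = 3.3 points. Exact (Clopper-Pearson) 95% intervals:
- 15/30 = 50.0% (31.3-68.7)
- 16/30 = 53.3% (34.3-71.7)

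The shift occurs only if the patient had no qualifying window before the event.

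**The case against.** **The drug-switch tail is narrow.** A reader might infer that every switch yields a full 8-week window on the other drug. The documents do not support that. The cutoff is the earlier of two dates, and early discontinuers have EOT at discontinuation. The schedule of events, as far as it can be read, marks hematology and transfusion evaluation at EOT and not at the later follow-up visit. Protocol 10.1 does mention visits about 28 and 56 days after the last dose, so later data are possible but not assured. The half-life of 14.9-16.2 days in Protocol 7.3 (healthy volunteers) also means ACE-536 is still present for part of the tail. This stands, and it makes the tail the lesser gap.

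**The bias need not favour the drug.** Off-drug time can bring transfusion need back up, and a patient who needs hydroxyurea may be losing response. That holds for mean changes and possibly fixed-week rates. It does not hold for rolling-window rates, where a poor tail cannot cancel an earlier response.

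**Early responders are unaffected.** With up to 60 months of rolling windows, plus A536-04 data for direct rollovers (SAP 4.1), many patients may already have qualified before any such event. This stands and limits the size. Symptomatic splenomegaly is also excluded at entry, which makes an early splenectomy less likely.

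**Using all data is a legitimate estimand.** Efficacy is secondary and descriptive, and listings make such cases visible. But the SAP states no such estimand. It already removes transfusion-influenced hemoglobin and stops 56 days after the last dose, which points to an effect attributable to the drug. Listings do not change the reported rates.

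**Censoring duration at a switch may be informative.** If the switch reflects failing response, censoring there could overstate duration. This is correct, and the fix allows for it.

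**Conclusion.** The point holds, chiefly for splenectomy. Neither document says how an on-study splenectomy is handled in the efficacy derivation, and the rules as written credit later windows to ACE-536. The tail after hydroxyurea or a growth factor is a real but smaller gap, of at most 56 days.

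The size is unknown. The 3.3 points per patient rests on an assumed 30 TD patients and on no qualifying window before the event; it is not an estimate of the total effect. A reader might also infer up to five years of contaminated windows. That is only the ceiling for a splenectomy soon after Cycle 1 Day 1 in a patient dosed to the end. Nor do the documents show that all efficacy results are biased upward: the one-way argument covers rolling-window rates and the longest observed response.

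The primary safety objective is not affected. This is a cheap improvement to the analysis plan, not a flaw in the study's main purpose.

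**What to change.** In SAP 5.7:

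- End each patient's efficacy windows at the earliest of the current cutoff, the date of on-study splenectomy, and the first recorded dose of hydroxyurea or a hematopoietic growth factor.
- Use recorded dates and send partial dates to medical review. The imputation in SAP 5.12.4 should not drive this cut: it sets a missing month to January and a wholly missing start date to informed consent, which could delete valid on-drug windows.
- For duration of response, count the start of hydroxyurea or a growth factor as the end of response in the main analysis, and show censoring at that date as a sensitivity analysis. Censor at splenectomy.
- Report the current cutoff rule as a sensitivity analysis, with the number of patients whose responder status differs.

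The cost is SAP wording, some programming, and medical review of a few dates; medications and procedures are already coded and listed (SAP 5.6). The downside is slightly less follow-up, and possibly a slightly lower response rate, in a few patients. No clinical rule changes.
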